# AEs

- AE description
  - o AESI
    - Immunosuppressant drug concentration level increased
    - Tissue-invasive CMV disease
    - Relapse or progression of the underlying disease for which the transplant was performed
    - Taste disturbance (dysgeusia)
    - Nausea
    - Vomiting
    - Diarrhea
    - Invasive fungal or bacterial infections
    - GVHD
- Start/end dates
- Serious AE/nonserious AE
- AE severity
  - o Mild

#### 02 June 2023

- o Moderate
- o Severe
- Outcome of AE
  - o Fatal
  - Not recovered/not resolved
  - Recovered/resolved
  - o Recovered/resolved with sequalae
  - Recovering/resolving
  - o Unknown
- Relatedness to maribavir
  - o Related
  - Not Related

## 6.4.3 Pre Index

#### Medical history

- Chronic kidney disease history
  - Date of diagnosis of chronic kidney disease
- ESRD characteristics
  - Date of ESRD diagnosis
  - Etiology of ESRD
  - eGFR at ESRD diagnosis
- Dialysis history
  - o Type
    - Peritoneal
    - Hemodialysis
  - Start/end dates of dialysis
- CMV infection history
  - Date of onset of infection/diagnosis
  - Refractory characteristics
    - Antiviral agent to which CMV infection is refractory
    - Type of drug-resistant mutations (if applicable)
  - Classification of CMV infection
    - Asymptomatic
    - Tissue-invasive CMV disease
    - CMV syndrome
  - Prior anti-CMV prophylaxis and treatment
    - Description of prophylaxis/treatment
    - Start/end dates
    - AEs including renal toxicity from prior anti-CMV treatment
- Transplant history
  - Number of transplants prior to the current transplant
  - Date of transplant(s)
  - Type of transplant(s)
    - HSCT
      - Autologous

Takeda TAK-620-4007 Protocol Maribavir

02 June 2023

- Allogeneic
- SOT
  - Heart transplant
  - Lung transplant
  - Liver transplant
  - Pancreas transplant
  - Intestine transplant
  - Kidney transplant
  - Other transplant
- Reason for transplant(s) (underlying disease)
  - Leukemia (acute myeloid)
  - Leukemia (chronic myeloid)
  - Leukemia (acute lymphocytic)
  - Lymphoma (non-Hodgkin's)
  - Myelodysplastic syndrome
  - Other myeloid malignancy
  - Other
- Stem cell source (for HSCT)
  - Bone marrow
  - Peripheral blood stem cell
  - Cord blood
  - Other
- o CMV serostatus of donor and recipient at each transplant
  - Donor positive/recipient positive
  - Donor negative/recipient positive
  - Donor positive/recipient negative
  - Donor negative/recipient negative

#### 6.4.4 Index

Patient demographics

- Year of birth
- Sex
- Ethnicity/race
  - o Asian
  - o Black
  - Hispanic
  - White
- Age at maribavir treatment initiation

#### Disease characteristics (at index)

- Current chronic kidney disease status
  - o eGFR
  - Chronic kidney disease stages
  - Dialysis status (type, start date)

Takeda TAK-620-4007 Protocol Maribavir

#### 02 June 2023

- Current CMV infection
  - Date of onset of infection/diagnosis
  - Refractory characteristics
    - Antiviral agent to which CMV infection is refractory
    - Type of drug-resistant mutations (if applicable)
  - Agent that patient is refractory to
  - o Classification of CMV infection
    - Asymptomatic
    - Tissue-invasive CMV disease
    - CMV syndrome
  - Prior anti-CMV medication used to treat the current CMV infection
    - Induction and maintenance therapy received for transplant, rejection treatment, and other adjuvant/related therapy
    - Start/end dates
    - Other anti-CMV prophylaxis and treatment
    - Other anti-infective agents
  - AEs including renal toxicity from prior anti-CMV treatment
- Current transplant status
  - Date of transplant
  - Type of transplant
    - HSCT
      - Autologous
      - Allogeneic
    - SOT
      - Heart transplant
      - Lung transplant
      - Liver transplant
      - Pancreas transplant
      - Intestine transplant
      - Kidney transplant
      - Other transplant
  - Reason for transplant
    - Leukemia (acute myeloid)
    - Leukemia (chronic myeloid)
    - Leukemia (acute lymphocytic)
    - Lymphoma (non-Hodgkin's)
    - Myelodysplastic syndrome
    - Other myeloid malignancy
    - Other
  - Stem cell source (for HSCT)
    - Bone marrow
    - Peripheral blood stem cell
    - Cord blood
    - Other

02 June 2023

- o CMV serostatus
  - Donor positive/recipient positive
  - Donor negative/recipient positive
  - Donor positive/recipient negative
  - Donor negative/recipient negative
- Current GVHD status (for HSCT patients only)
  - Acute GVHD status
    - Presence
    - Absence
    - Grade
  - Chronic GVHD status
    - Presence
    - Absence
    - Grade
- Relevant comorbidities ongoing or diagnosed at index date and treatment

## Concomitant medications ongoing or starting at index date

- Drug name
- Start/end dates

#### 6.4.5 Post index

#### CMV status

- Resolved
  - Date of resolution
- Unresolved

## Concomitant medications

- Drug name
- Start/end dates

## Dialysis treatment during maribavir treatment

- Type and frequency
- Changes in dialysis treatment Reason for change

#### Patient status

- Death
  - Date of death
  - Primary cause of death
- Lost to follow-up
  - Date of loss to follow-up

# 6.5 Study Size

The source population for the current PASS comprises of post-transplant patients with CMV infection/disease refractory (with or without resistance) to prior antiviral treatments and a post-transplant diagnosis of comorbid ESRD or comorbid severe chronic renal disease requiring peritoneal dialysis or hemodialysis. As such, study size will be dependent on the patterns of use of maribavir in routine clinical practice during the first years after launch for an indication that is expected to be ultra rare.

Considering the eligibility criteria, coupled with the rarity of the source population, the target sample size for this PASS is approximately 10 patients. This target sample size was determined by practical and feasibility assessments, and findings from the pivotal SHP620-303 (SOLSTICE) trial. Of the 352 randomized patients in the SOLSTICE trial, only 11 patients with 8 (2.3%) on maribavir treatment had severe chronic renal disease, defined as creatinine clearance <30 mL/minute according to the Cockcroft-Gault formula (Avery et al. 2022; Sampson and Drury 1992). Notably, patients in the SOLSTICE trial were not on dialysis; the current study aims to further select patients from an already rare population. Although no formal hypotheses have been prespecified and sample size calculations are not applicable, best estimates and 95% confidence intervals (CIs) for various sample sizes are presented in Table 3.

	Sample Size		
% of Participants with AEs	10	20	
5%	38.1% (0%, 38.1%)	24.7% (0.1%, 24.9%)	
20%	53.1% (2.5%, 55.6%)	37.9% (5.7%, 43.7%)	
35%	60.4% (9.3%, 69.6%)	43.8% (15.4%, 59.2%)	
50%	62.6% (18.7%, 81.3%)	45.6% (27.2%, 72.8%)	
65%	60.4% (30.4%, 90.7%)	43.8% (40.8%, 84.6%)	
80%	53.1% (44.4%, 97.5%)	37.9% (56.3%, 94.3%)	
95%	38.1% (61.9%, 100%)	24.7% (75.1%, 99.9%)	

# Table 3Best Estimate and 95% CIs for a Population Proportion According to
Expected Patient Counts for Different Possible AE Rates

## 6.6 Data Management

Data management will be conducted in accordance with the data management plan. This plan will be developed and approved before finalizing the design of the study database that provides data collection tools to the site. The data management plan will address processes, responsibilities, and resources for data handling during the study and after completion; types of data and data sources; ethics; storage, back up and security; and data sharing/data use agreements.

#### Takeda TAK-620-4007 Protocol Maribavir

02 June 2023

The sponsor will provide a password-protected, web-based EDC system to serve as an integrated, transparent tool to collect and manage data and track study progress at the center and patient level. Data in the EDC system will be kept in a central location, and all data will be transmitted to a central database.

For the chart review, information from patient medical records will be collected by study sites and entered directly into the eCRF. There will be 2 waves of data extraction, during which the sites will be invited to perform data extraction of eligible patients into the eCRF. Prior to the start of data extraction, sites will be fully trained to use the online EDC system and will receive eCRF completion guidelines. Sites will be responsible for entering abstracted patient data into a secure, internet-based EDC study database via the eCRF. Investigators and authorized site personnel will be able to access their account with a username and password. All eCRFs should be completed by the investigator, study coordinator, or designated trained personnel, as appropriate. All changes or corrections to the eCRFs will be documented in an audit trail and an adequate explanation will be required.

The EDC system will include logic checks to minimize data entry errors. Data inconsistencies outside the logic checks will be managed by manual queries issued by data management within the EDC system for site completion. All queries will be monitored until there is a resolution within the EDC through the electronic query report.

After all study data are abstracted and reviewed, in accordance with the data management plan, the database will be locked and transferred to the sponsor or designate. Takeda will file a validated copy of the study database after database lock.

To enable evaluations and/or audits from regulatory authorities or the sponsor, the investigator agrees to keep records, including the identity of all participating patients (sufficient information to link records [eg, eCRFs and medical records]), source documents, detailed records of patient disposition, and adequate documentation of relevant correspondence (eg, letters, meeting minutes, and telephone calls/reports). The records should be retained by the investigator for the length of time specified in local regulations or in the site contract agreement (whichever time period is longer).

If the investigator is not available (eg, retirement or relocation) to continue to retain the study records for the required period, the sponsor should be notified. The study records must be transferred to a designee approved by the sponsor, such as another investigator, another institution, or an independent third party arranged by the sponsor. The investigator must obtain the sponsor's written permission before disposing of any records, even if retention requirements have been met.

## 6.6.1 Data Collection Tool

The sponsor will provide a web-based EDC system (Medidata RAVE system) to serve as an integrated, secure, transparent, and validated tool to collect and manage data and track study progress at the site and patient level. Data in the EDC system will be kept in a central location and all data will be transmitted to a central database.

#### Takeda TAK-620-4007 Protocol Maribavir

The EDC system will meet approved and established standards for the security of health information, be validated, and be 21 Code of Federal Regulations Part 11 compliant. To ensure that patient data (as well as other confidential data) remain secure and intact, standard operating procedures and quality control processes that address patient data security will be followed. The EDC system will have built-in edit checks and validations and will support electronically generated and manual queries.

The study site investigator must provide a signature to confirm the collected data.

# 6.6.2 Data Flow

The data flow for this chart review study is summarized below:

- The source for data collected will be patient medical records (electronic and/or paper charts) that are stored at the site.
- Site staff will be trained by the contract research organization (CRO) to perform the chart abstraction, including data entry and how to retrieve and respond to data queries in the EDC system. It is assumed that all sites will be able to complete data entry into the eCRFs via the EDC system.
- The EDC system will include logic checks to minimize data entry errors. Data inconsistencies outside the logic checks will be managed by manual queries issued by data management within the EDC system for site completion. All queries will be monitored until resolution within the EDC through the electronic query report.
- Each study investigator has the ultimate responsibility for the collection and reporting of all data entered in the eCRFs and any other data collection forms (source documents), and ensuring that they are accurate, authentic/original, attributable, complete, consistent, legible, timely (contemporaneous), enduring, and available when required. The eCRFs must be signed before database lock by the study investigator attest that the data contained are correctly recorded.
- The data entered into the EDC system will contribute to a custom study database for the purpose of analysis in this study.

# 6.7 Data Analysis

The statistical analysis of the data will be primarily descriptive, without prespecified hypotheses, but inferential statistics will be used to estimate the precision around descriptive estimates (eg, 95% CI), if the sample size allows. The final analyses will be performed once the data from all patients has been collected in the database, cleaned, and database lock has occurred. Post hoc analyses may be completed to support planned study analyses, and these will be clearly identified as such in the clinical study report.

Full details on data transformations/derivations, categorical definitions, subgroup analyses, handling of missing data and censoring, and presentation of results will be described separately in the SAP, which will be developed and finalized before any planned analysis. The final SAP will include table shells to be populated during the analyses.

For purposes of the summary tabulations, patient data will be pooled across all study sites. Stratifications by country are not foreseen. In general, data summaries will be presented overall and by the subgroups of interest where applicable.

Demographic and baseline characteristics will be summarized using descriptive statistics.

Medical Dictionary for Regulatory Activities (MedDRA) coding version 25.0 or later will be used to classify and tabulate AEs/adverse drug reactions (ADR). Frequencies (absolute and percentages) across system organ class (SOC), for individual events within those classes and preferred terms (PT), will be provided and calculated with 95% CIs.

All statistical analyses will be performed using SAS version 9.4 or higher or SAS Enterprise Guide version 7.1 or later (SAS Institute, Cary, NC 27513).

# 6.7.1 Statistical Methods

Unless otherwise specified, all statistical analyses will be descriptive in nature. Continuous variables will be described by the number of eligible participants and missing data, mean, standard deviation, median, first quartile, third quartile, and minimum and maximum values. Categorical variables will be described as the total number of participants and relative percentage per category. Percentages will be calculated using the most appropriate denominator. Two-sided 95% CIs will be reported as appropriate.

Should missing data occur, missing data will not be imputed and the data will be analyzed as they are recorded in the study eCRFs. However, for all missing dates, some date imputation may be performed. The general imputation rules will be described in the SAP. Missing data may be included as a separate category in some cases, depending on the nature of the variable. Unless otherwise specified in a table's footnote, missing values will not be included in the denominator for summarizing a categorical variable's distribution. If the eCRF includes a selection of "unknown," these responses will not be considered missing responses and will be included in the distributions.

Descriptive analysis will be performed on the variables listed in Section 6.4. Year of birth will be analyzed as age and age group, and dates would be as duration or index days/weeks. Detailed definitions of additional variables that may be derived from the collected data for the statistical analysis will be included in a separate SAP.

Incidence of each outcome will be expressed per person-year of exposure to account for varying length of follow-up. Incidence rates will be calculated as the number of patients with an event of interest, divided by the number of person-years at risk, ie, the summed person-year of maribavir exposure. Only new cases will be included in the numerator; patients with existing AEs at the index date who reported the AE before the index date will not be counted, and patients who initially experience AEs at index or at the post index date will be counted only once in the numerator (ie, worsening outcomes will not be counted as new cases). The following definitions will be used to estimate incidence rates:

- Person-days at risk for an individual will be defined as the total number of days of maribavir exposure (ending at the date of the outcome of interest, the final dose of maribavir +7 days, death, or end of data availability). For each incidence rate, 95% CIs will be calculated using exact methods.
- The follow-up period (person-days) will be defined as the period from the index date until the earliest of: 7 days following the date of discontinuation of initiated maribavir medication, end of data availability, or death.
- Person-years will be calculated by dividing person-days by 365.

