## 6.4 Variables

All data collected in the study will be transferred into variables. Completeness of all variables may be dependent on country-specific data privacy regulations (eg, ethnicity/race). Detailed definitions of additional variables that may be derived from the collected data for the statistical analysis will be included in a separate statistical analysis plan (SAP).

The following variables will be collected at the pre-index, index, and post index periods subject to availability in the medical charts. The exposure variables capture the maribavir treatment regimen and the outcome variables capture all safety data. All other variables from this study will be presented by time period.

Current CMV infection and current transplant refer to the latest CMV infection and transplant for which the maribavir treatment was initiated.

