# 6.7.1.1 **Primary Objective**

Incidence rates (number of first events per person-year at risk) of AEs and ADRs (overall, and by SOC and PT) after administration of maribavir over the follow-up period will be computed along with 95% CIs. The number and percentage of patients with AEs and ADR, total number of AE and ADR, and AEs and ADR rate (total number of each event per person-year) will also be summarized.

The distribution of AEs by severity, seriousness, outcome, and physician's causal assessment will be tabulated.

Analyses will be based on the evaluable safety population, defined as patients who receive at least 1 dose of maribavir.

Subgroup analyses may be performed by select baseline characteristics, treatment conditions, and any other variables of interests. Subgroup analyses may be identified post hoc during analysis.

Listings of individual participants data of the AEs and serious AEs, as well as the narrative statements of events, will be reported.

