# 6.7.1.2 Secondary Objective

Incidence rates (number of first events per person-year at risk) of each AESI after administration of maribavir over the follow-up period will be computed along with 95% CI. The number and percentage of patients with each AESI, total number of each AESI, and AESI rate (total number of each event per person-year) will also be summarized.

The distribution of AESI by severity, toxicity, seriousness, and physician's causal assessment will be tabulated.

Listings of individual participants data of the AESIs, as well as the narrative statements of events, will be reported.

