## 6.8.1 Data Validation

Data collection procedures will be reviewed with site personnel during site initiation. Data will be validated at the point of entry through the EDC platform using soft and hard stops to maximize the degree of clean and complete data when published to the database.

Plausible value ranges for numerical data, logical data, and list entries will be filed in the eCRF. Tests for consistency and completeness based on these conditions will be performed during data entry in the eCRF. The validity of the recorded data will therefore be ensured by the validations incorporated in the documentation system, which highlight incorrect or implausible entries to the individual entering the data.

Edit checks include data type (integer, decimal, text), range, length (maximum characters or number length), precision (decimal places), date ranges, missing data in required fields, and overlapping data. In addition, data can be compared against absolute values (eg, study start), values on the same screen, values in other data entry sessions, calculated (dynamic) values, and multiple values. Corrections made after the data are saved will be documented in an audit trail.

The clinical data manager will review data issues raised by online and post-entry checks using validation programs and data listings. Since all data will be collected retrospectively, most queries will address data entry errors. Information that is not in the medical record will not be queried.

If clarifications are needed, data queries will be created through the web-based application. Site personnel will be required to respond to the queries and correct the study database, if needed. The site investigator will retain full responsibility for the accuracy and authenticity of all eCRF data. Additional details will be delineated in the data management plan.

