### 6.9 Limitations of the Research Methods

Due to the rare occurrence of the population of interest, a small sample size is projected that limits the precision of estimates. To maximize the sample size, the study will aim to include all available and eligible patients at the site rather than limiting enrolment by site or country.

Several factors may impact the sample size, notably maribavir market launch and uptake in the different European countries. Monitoring of patient inclusion at the site and country levels will allow the deployment of mitigation strategies in response to any challenges. Such plans will be discussed by the marketing authorization holder and the Pharmacovigilance Risk Assessment Committee. They may include the initiation of additional sites within the participating countries and/or expanding the study into other countries.

Given the retrospective nature of this study, data quality and completeness will be dependent on the quality, eg, accuracy and comprehensiveness, of the information reported in the medical records and the accuracy and consistency of data entry in the eCRF by investigators. In addition, availability of information in records may vary by physician practice and will reflect differences in practice patterns, recording practices, and medical norms. The eCRF will be designed to minimize the level of missing data collected. Additionally, data collectors will be given detailed guidance for accurate completion of the eCRF. Remote central monitoring will be conducted promptly after data entry so that queries can be raised in a timely manner. In addition, the EDC system includes edit checks designed to deliver data that is predominantly clean upon data entry. Missing exposure and outcome dates in the medical record will not be imputed to avoid information bias.

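### AESIs enter the data only when charted, so a silent chart works as no event; charted AESI incidence is probably a lower bound and documentation status should be recorded

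*Protocol*

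**What the plan says.** **What is collected.** Section 6.4 makes all data depend on the charts: "The following variables will be collected at the pre-index, index, and post index periods subject to availability in the medical charts". Section 6.4.2 places the nine AESIs under the adverse event description, followed by dates, seriousness, severity, outcome and relatedness. Each of these describes an event that has been found. No listed item records whether the chart addresses the AESI at all.

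**What happens to silence.** Section 6.8.1: "Information that is not in the medical record will not be queried".

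**What is reported.** Section 6.7.1.2 plans "The number and percentage of patients with each AESI", with event counts and rates. It names no denominator of its own. Section 6.7.1.1, under the primary objective, says: "Analyses will be based on the evaluable safety population, defined as patients who receive at least 1 dose of maribavir". Section 6.7.1 divides patients with an event by the summed person-years of exposure, with no condition that the symptom was assessed.

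**The missing-value rule.** Section 6.7.1 says that "missing values will not be included in the denominator for summarizing a categorical" variable, unless a table footnote states otherwise. The same section also leaves the choice of the most suitable denominator open.

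**The stated limitation.** Section 6.9 concedes that "availability of information in records may vary by physician practice and will reflect differences in practice patterns, recording practices, and medical norms". It does not say which way this moves AESI incidence.

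**The concern.** A chart that documents the absence of nausea and a chart that never mentions nausea leave the same empty record. Both patients stay in the denominator and neither reaches the numerator. The error goes one way, towards reassurance.

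It matters most where charting depends on habit. Section 4 gives diarrhea, dysgeusia, nausea and vomiting as examples of the most common adverse events of maribavir; these are four of the nine AESIs, and all are symptoms. An increased immunosuppressant level raises a similar problem: it cannot appear if no level was measured.

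The study exists to fill a gap listed as missing information in the EU Risk Management Plan, and Section 6.5 says "the target sample size for this PASS is approximately 10 patients". A line such as 0 of 10 with taste disturbance would be read as evidence of absence. As planned, the report could not show whether taste was mentioned in ten charts or in four.

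**Working it through.** **Inputs.** From the protocol: N of about 10 (Section 6.5) and two-sided 95% intervals (Section 6.7.1: "Two-sided 95% CIs will be reported as appropriate"). Assumed, because the protocol gives no figure: 10% to 50% of events uncharted, and 2 to 5 of 10 charts silent on a given AESI.

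**1. Reproduce the plan's own figure.** Table 3 gives a width of 53.1% and limits of 2.5% and 55.6% for 20% at N = 10. The exact Clopper-Pearson limits are the 2.5% quantile of Beta(x, N − x + 1) and the 97.5% quantile of Beta(x + 1, N − x). With x = 2 and N = 10 they are 2.5% and 55.6%, width 53.1%. All 14 cells of Table 3 reproduce this way, taking x = p × N and allowing non-integer x. The table is not in dispute; this only fixes the interval method used below.

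**2. Expected value of the planned percentage.** Let p be the true risk and s the probability that an event is charted, with false entries negligible. The all-patient percentage then estimates p × s. For p = 35%:

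- s = 90%: 0.35 × 0.90 = 31.5%
- s = 70%: 0.35 × 0.70 = 24.5%
- s = 50%: 0.35 × 0.50 = 17.5%

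The rate moves the same way. An uncharted event is lost from the numerator, and the patient's person-time runs on where Section 6.7.1 would have stopped it at the event.

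**3. Range left open by silent charts.** With x charted events and u patients of undocumented status, the proportion lies between x/N and (x + u)/N. For x = 2 and N = 10:

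- u = 2: 20% to (2 + 2)/10 = 40%
- u = 3: 20% to (2 + 3)/10 = 50%
- u = 5: 20% to (2 + 5)/10 = 70%

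**4. No charted event.** The exact upper limit for 0/10 is 1 − 0.025^(1/10) = 30.8%. If 5 of those 10 charts were silent, the range from silence alone would be 0% to 5/10 = 50%, which goes beyond that limit. The confidence interval covers sampling error only.

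**5. Does dropping silent charts repair the estimate?** For x = 2, leaving out 2, 3 or 5 silent charts gives 2/8 = 25% (3.2% to 65.1%), 2/7 = 28.6% (3.7% to 71.0%) and 2/5 = 40% (5.3% to 85.3%). Let c be the probability that absence is charted in an event-free patient. The documented-only proportion then estimates p·s / [p·s + (1 − p)·c]. With p = 35% and s = 70%:

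- c = 20%: 0.245 / (0.245 + 0.130) = 65.3%
- c = 50%: 0.245 / (0.245 + 0.325) = 43.0%
- c = 80%: 0.245 / (0.245 + 0.520) = 32.0%

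The result can lie well above or somewhat below the true 35%. It is neither an unbiased estimate nor a bound.

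**The case against.** **No rule is broken.** A reader might infer that counting silent charts in the full denominator contradicts the missing-value rule in Section 6.7.1. The documents do not support that. The rule concerns the distribution of a categorical variable, yields to table footnotes and stands beside a free choice of denominator. Event incidence has its own definition in the same section. An event that was never charted creates no record and no missing field. This objection stands in full.

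**It belongs to the SAP and the eCRF.** Section 6.7 leaves missing-data handling and table shells to the SAP, and the eCRF is not shown. Section 6.7.1 also foresees eCRF answers of unknown. This stands in part: the full-denominator reading is inferred from several sections, and Section 6.7.1.2 does not spell it out. But the listed variables are set in Section 6.4.2, and no analysis rule can recover a documentation status that was never abstracted. No AESI occurrence field is listed in which unknown could be chosen. The needed structure is already used elsewhere: Section 6.4.4 records GVHD at index as present or absent, with grade.

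**It is inherent and already conceded.** A retrospective review cannot query what was never written, and Section 6.9 admits dependence on recording practices. Section 8.2 also promises systematic identification of endpoint events. True, but systematic abstraction finds only what is written, and Section 6.9 neither ties the caveat to AESI incidence nor names its direction.

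**Conclusion.** The point holds as a cheap improvement, not as an internal contradiction. On the listed variables and stated denominators, a silent chart works as no event, and AESI incidence is probably a lower bound. This is clearest for the four symptom AESIs and for immunosuppressant levels that were never measured; the argument is weaker for events that are likely to be charted whenever they occur.

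The size cannot be derived from the protocol. If 10% to 50% of events go uncharted, a true 35% reads as 31.5% to 17.5%. If 5 of 10 charts are silent and 2 show the event, the data fit anything from 20% to 70%. These figures assume negligible false entries and illustrative counts.

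A further inference to resist is that the documented-only proportion caps the truth. In the example it is 40%, while the actual upper bound is 70%.

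**What to change.** - **Section 6.4.2:** add one status item per AESI for the follow-up window: occurred, documented absent, not documented, or not applicable (for example GVHD after solid organ transplant). For immunosuppressants, also record whether a level was measured.
- **Section 6.7.1.2:** keep the all-patient percentage as the main figure, label it charted incidence, and show the number of patients with undocumented status beside it. If bounds are wanted, use x/N and (x + undocumented)/N. Do not present the documented-only proportion as a bound.
- **Section 6.9:** state that incomplete charting biases AESI incidence downward.

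The cost is nine more items per chart, about 9 × 10 = 90 entries in all, plus one table column and one sentence. The items need to be in place before abstraction starts, planned for about June 2025. The limit of the fix is that absence is charted selectively, so the status item describes documentation and does not correct the estimate.
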